8.6 Vital Signs, Physical Findings, and Other Observations Related to Safety

8.6.1 Vital Signs

Values at Visit 3 (At Randomization), At First Dose, and at 3 Weeks Post First Dose, as described in Section 3, in systolic blood pressure, diastolic blood pressure, heart rate, respiratory rate, and temperature will be summarized by treatment group for the safety population using descriptive statistics.

Vital sign values will be presented in a data listing for all subjects in the safety population.

8.6.2 Physical Examinations

A physical examination will be performed at study visits 3, 6, 9, and 10. An indication of whether the examination was performed, date of the examination, and an indication of whether abnormal findings that were clinically significant were found will be collected. Because details of clinically significant abnormal findings will be entered on the medical history or AE form as appropriate, this data will be summarized with medical history and AEs, respectively.

8.6.3 Other Safety Measures

8.6.3.1 Prior and Concomitant Medications

The prior and concomitant medications will be coded using the latest version of World Health Organization Drug Dictionary (WHO Drug) Global Version (September 2018) to identify the drug class and preferred drug name.

Concomitant medications will include all medications that started on or after day of first dose of the study treatment in the first period or that stopped on or after day of first dose of study treatment in the first period. Prior medications will include all medications that started and stopped prior to the day of first dose of the study treatment in the first study period.

Concomitant medications will be categorized as occurring in study period 1 or study period 2. Concomitant medications that started or stopped on or after day of first dose of study treatment in period 1 and before the start of period 2 are attributed to period 1. Concomitant medications that started prior to the first dose of study treatment in period 1 and stopped on or after day of first dose of study treatment in period 1, or are ongoing, are attributed to period 1. Concomitant medications that started or stopped on or after day of first dose of study treatment in period 2 are attributed to period 2. Concomitant medications that started prior to the study and are stopped on or after day of first dose of study treatment in period 2, or are ongoing, are attributed to period 2.

The number and percentage of subjects using prior and concomitant medications will be tabulated for each study period by Anatomical Therapeutic Chemical (ATC) level 1 term, ATC level 2 term, and preferred drug name for all subjects in the safety population. If a subject has more than 1 medication within an ATC level 1 term, the subject will be counted only once in that ATC level 1 term. Similarly, if a subject has more than 1 medication within an ATC level 2 term, the subject will be counted only once in that ATC level 2 term. If a subject has more than 1 medication that codes to the same preferred drug name, the subject will be counted only once for that preferred drug name. All percentages will use the number of subjects in the safety population as the denominator. The tabular summary will be sorted by descending frequency by ATC level 1 term, ATC level 2 term, and preferred drug name.

Prior medications will be summarized overall by planned treatment sequence. Concomitant medications will be presented by actual treatment group and overall with percentages that use the number of subjects in the safety population as the denominator. Prior and concomitant medication data will also be presented in a data listing for subjects in the safety population.

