## 8.3 Second Treatment Period (Visits 7 [T], 8 [T] and 9)

The second treatment period will begin once patients have passed their second blue dye marker at the end of V6, and the stool sample collection is complete. As soon as this has occurred, patients will crossover to their new treatment (either MS1819-SD or patient's prestudy porcine PERT).

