If the patient has not passed the first blue dye marker within 4 days after ingesting the first dye marker capsules, or within 2 days after ingesting the second dye marker capsules, then 5-10 mg of oral bisacodyl may be given. Bisacodyl is the only laxative that may be given during the marker-to-marker stool collection period. Note: Patients on a stable chronic osmotic laxative may continue this therapy during the marker-to-marker stool collection.

The supervised confinement may take place within an inpatient facility or within an alternative confinement setting. This will be discussed and approved on an individual case basis by the sponsor. The alternative confinement setting will require the supervision of trained study site staff to oversee the study procedures.

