8.3 Adverse Events

Adverse events will be coded using the Medical Dictionary for Regulatory Activities (MedDRA) Version 21.1 to identify the system organ class and preferred term.

Adverse events that occur or are reported to worsen in severity on or after date of first dose of study treatment in period 1 will be considered to be TEAEs.

TEAEs will be categorized as occurring in either study period 1 or study period 2 according to the following rules:

- Adverse events that occur or are reported to worsen in severity on or after date and time of start of period 1 study treatment and on or before date and time of end of period 1 study treatment will be attributed to study period 1. Adverse events that occur or are reported to worsen in severity on the start date of period 1 study treatment that do not have a time associated with the event will be attributed to study period 1.
- Adverse events that occur or are reported to worsen in severity after the end date of period 1 study treatment and on or before the date of end of period 2 study treatment will be attributed to study period 2. Adverse events that occur or are reported to worsen in severity on the date of end of period 2 study treatment that do not have a time associated with the event will be attributed to study period 2.

- Adverse events that occur on the crossover date between study period 1 and study period 2 that do not have a time associated with the event will be attributed to study period 1.
- Adverse events that occur in both study period 1 and study period 2 will be attributed to both study periods.

TEAEs that occurred after the subject's last study period will be classified as follow-up TEAEs. If a subject entered both the first and second study periods, any event occurring after the end date of the second study period will be considered a follow-up TEAE. If a subject discontinued prior to the start of the second study period, any event occurring after the end date of the first study period will be considered a follow-up TEAE.

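### SAP 8.6.3.1 assigns medications on the crossover date to Period 2 by calendar day, unlike the adverse event rule in SAP 8.3, so a drug finished before a same-day switch is counted under a treatment not yet begun

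*SAP*

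**What the plan says.** Medications (SAP 8.6.3.1). Period 1 takes medications that started or stopped from the day of its first dose "and before the start of period 2 are attributed to period 1"; whether that limit is a day or a moment is not stated. Period 2 is defined by calendar day: "Concomitant medications that started or stopped on or after day of first dose of study treatment in period 2 are attributed to period 2". A fourth attribution sentence uses the same day-based cut-off for drugs begun before the study. The period decides the treatment column, because "Concomitant medications will be presented by actual treatment group and overall".

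Adverse events (SAP 8.3). An event "on or before date and time of end of period 1 study treatment will be attributed to study period 1". Untimed events on the crossover date have their own rule: those "that do not have a time associated with the event will be attributed to study period 1".

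Crossover (Protocol 8.3). Period 2 begins when the second dye marker has passed at the end of Visit 6: "As soon as this has occurred, patients will crossover to their new treatment". Protocol 7.1 specifies no washout.

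Laxative use (Protocol 8.3.3.1). "Bisacodyl is the only laxative that may be given during the marker-to-marker stool collection period". One of its two triggers is that 2 days have gone by since the second marker capsules. A patient in that position at Visit 6 is still on the first treatment.

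**The concern.** The two safety rules treat the same day differently. With an immediate switch, one date can hold both the end of the first treatment and the first dose of the second. The adverse event rule deals with that overlap and the medication rule does not. A drug that was finished before the switch can therefore appear in the column of a treatment the patient had not yet started.

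SAP 8.1 summarizes safety by actual treatment so that tolerability can be compared within patients, and it lists concomitant medications among the measures. Laxative use bears on that comparison: Protocol 5.6.1 reports constipation in 2 patients given the freeze-dried form of the lipase. If use before the switch is added to, or moved to, the other column, the medication table blurs a contrast it is meant to show. It can also disagree with the adverse event table for the same patient and day.

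**Working it through.** The plan gives no figure to reproduce. The check is to apply both sets of rules to the same records.

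**Inputs**
- Adverse events: Period 1 closes by date and time; untimed on the crossover date goes to Period 1 (SAP 8.3).
- Medications, Period 1: must fall before the start of Period 2, with day or time unstated (SAP 8.6.3.1).
- Medications, Period 2: any start or stop on or after the calendar day of the first Period 2 dose (SAP 8.6.3.1).
- Period 2 begins when the second marker passes (Protocol 8.3).

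**Assumed crossover day.** A drug is taken at 09:00 on the first treatment, the second marker passes at 14:00, and the first Period 2 dose is at 18:00 on the same date. The clock times are illustrative; only their order and the shared date matter.

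**Result under two readings of the start of Period 2**

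| Record | Start is a calendar day | Start is the time the marker passes |
|---|---|---|
| Untimed adverse event on the crossover date | Period 1 | Period 1 |
| Drug started and stopped at 09:00 on the crossover date | Period 2 only | Periods 1 and 2 |
| Drug started the day before, stopped at 09:00 on the crossover date | Periods 1 and 2 | Periods 1 and 2 |
| Drug started and stopped the day before | Period 1 only | Period 1 only |

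The reading settles only whether Period 1 also counts the drug in the second row. The Period 2 sentence refers to the day of first dose, so it captures the second and third rows whichever reading is taken.

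**What this could do to a table.** The counts here are assumed and do not come from the documents. The 38 planned patients give 38 / 2 = 19 per sequence. Suppose 4 patients in the MS1819-first sequence and 1 in the PERT-first sequence take one dose of bisacodyl on the crossover date before the switch.
- True use by treatment: 4 on MS1819, 1 on PERT.
- Calendar-day reading: the 4 move to PERT and the 1 moves to MS1819, so the table shows 1 on MS1819 and 4 on PERT.
- Time reading: all 5 are counted under both, so each column shows 4 + 1 = 5.

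The true difference of 4 − 1 = 3 becomes 1 − 4 = −3 on the first reading and 5 − 5 = 0 on the second.

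**The case against.** The best defence is that Protocol 8.3 ties the start of Period 2 to an event, the passing of the second marker. A drug given while waiting for that marker then precedes Period 2 and is caught by the Period 1 sentence, so it is counted under both treatments and not moved. Counting generously by day is a recognizable convention, and the SAP is inclusive elsewhere: ongoing drugs count in both periods, and a fully missing start date is imputed for each period. This stands in part. A reader might infer that every one-day drug taken before the switch is counted only under the wrong treatment. The text does not support that, because it holds only if the start of Period 2 is a day. The defence does not remove the problem, since the Period 2 sentence still credits a finished drug to a treatment not yet begun.

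The bisacodyl example also depends on timing that the documents do not fix. A dose given and stopped the day before crossover stays in Period 1. MS1819-SD is taken with food, so a marker that passes late in the day may put its first dose on the next date, and then nothing overlaps. How often the dates coincide is not stated, although the SAP foresees a shared date by giving adverse events a rule for it: "Adverse events that occur on the crossover date between study period 1 and study period 2 that do not have a time associated" is how that rule opens.

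Finally, a reader might infer that an adverse event and the drug given for it that day always fall in opposite columns. That needs an untimed event, a drug finished before the switch, and the calendar-day reading. On the time reading the drug also appears beside the event. A drug started on the crossover date and continued afterwards belongs in Period 2 in any case.

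**Conclusion.** The point holds in limited form. Where the end of Period 1 treatment and the first Period 2 dose share a date, a medication finished that day before the switch is counted under the second treatment on every reading. Whether it is also counted under the first depends on an undefined term. A Period 1 medication stopped that day is counted under both on either reading. This is a stated rule that gives a wrong attribution, and it differs from the SAP's own rule for adverse events; SAP 11.1 does not discuss the difference.

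The size is small. The exposure is one calendar day per patient, at the Visit 6 crossover, in descriptive tables. The number of affected records cannot be derived from the documents. No test, analysis population or efficacy endpoint uses these attributions, so the CFA analysis is unaffected. The individual medication records are also listed, so a careful reader could trace the dates.

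**What to change.** In SAP 8.6.3.1:
- Define the start of Period 2 as the date and time of the first Period 2 dose. SAP 8.2 already plans to list this.
- Where a medication time is recorded, attribute by that time. A timed drug first taken after the switch then goes to Period 2.
- Where no time is recorded, a medication that started or stopped on the crossover date goes to Period 1, and counts in Period 2 as well only if it continued after that date.
- For untimed records, change the stop condition for Period 2 from on or after the day of first dose to after that day, in both the third and the fourth attribution sentences.

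The documents do not show whether medication times are collected. If they are not, the untimed rule covers every record and the fix still works.

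The cost is a few words in the SAP and a small programming change. The downside is that an untimed drug first taken after the switch and finished that day goes to Period 1, a compromise the SAP already accepts for adverse events.

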### 8.3.2 Visit 9: Stool Collection in Controlled Supervised Facility (Day 38 ± 7)

Patients will be admitted for a maximum of 7 days to a facility providing supervised confinement for collection of stools for determination of CFA, CNA and stool weight. The stool collection and dietary procedures will be conducted as described in Section 8.3.3.1 (Instructions for Supervised Confinement). The following procedures will be performed at Visit 9:

- Focused physical exam to evaluate gastrointestinal tract, heart, and lungs
- Record body height and weight
- Record vital signs while sitting (blood pressure, pulse rate, breathing rate, and temperature)
- Record any changes in AEs and concomitant medication
- Instruct/dispense study drug
- Verify study drug count on the last day of confinement
- Return MS1819-SD (only for patients that crossed over to MS-1819SD) on the last day of confinement
- Assess and record malabsorption signs and symptoms
- Begin 72-hour controlled diet

- Marker-to-marker stool collection and stool weight (central laboratory will weigh the stool that is collected)
- Collect urine sample for urinalysis
- Perform a urine pregnancy test (urine dip stick), if applicable
- Collect samples for hematology, clinical chemistry, PT/INR, and aPTT
- Collect samples for fasting lipids and prealbumin
- Collect blood samples for vitamin determination (A, D, E, and K)
- Collect a serum sample for circulating anti-LIP2 lipase antibodies and MS1819-SD concentrations
- At the end of the supervised confinement (once the second blue dye marker sample has been collected):
  - All patients are to resume therapy on their prestudy porcine PERT. Patients who crossed over to MS1819-SD will resume treatment on their prestudy porcine PERT; Patients who crossed over to their prestudy PERT will continue with their prescribed therapy.
  - Patients on MS1819-SD will return all study drug.
- Remind patients of their scheduled Visit 10 date

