8. SAFETY EVALUATION

8.1 Overview of Safety Analysis Methods

All safety analyses will be performed using the safety population and summarized by actual treatment (MS1819-SD regardless of period vs. PERT regardless of period) allowing direct intrasubject comparison of the tolerability of MS1819-SD vs. PERT. Safety measures summarized will include AEs, laboratory data, vital signs, and concomitant medications. Additionally, exposure to study treatment during the study will be displayed.

Safety data will not be imputed, except for partial and missing dates, which will be imputed only for defining treatment-emergent AEs (TEAEs) and concomitant medications. Imputed dates will not be presented in data listings.

TEAEs will be defined as any AEs that occur or are reported to worsen in severity on or after the date of first dose of study treatment in period 1. Partial dates will be imputed for the purposes of defining TEAEs as follows:

- For a missing start day where the month and year are present, the start day will be set to the first day of the month, unless 1) the first day of the month is before the date of first dose of study treatment and the month and year are the same as the month and year of the date of first dose of study treatment, and 2) the end date is on or after the date of first dose of study treatment or the end date is completely missing, in which case the start day will be set to the first day of first dose of study treatment.
- For a missing start day and month where the year is present, the start day and month will be set to January 1st, unless 1) January 1st is before the date of first dose of study treatment and the year is the same as the year of the date of first dose of study treatment, and 2) the end date is on or after the date of first dose of study treatment or the end date is completely missing, in which case the start day and month will be set to that of the date of first dose of study treatment.
- For a missing end day where the month and year are present, the end day will be set to the last day of the month, unless the month and year are the same as the month and year of the last contact date for the subject, in which case the end day will be set to that of the subject's last contact date.

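### SAP 8.6.3.1 gives Period 2 no end date for concomitant medications, so medications first started in follow-up are counted under the Period 2 treatment

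*SAP*

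**What the plan says.** SAP 8.6.3.1 defines concomitant medications with a start point only: "Concomitant medications will include all medications that started on or after day of first dose of the study treatment in the first period" (or stopped on or after that day). It offers two categories: "Concomitant medications will be categorized as occurring in study period 1 or study period 2". A medication that starts or stops from the first Period 1 dose "and before the start of period 2 are attributed to period 1", so that rule closes when Period 2 begins. The Period 2 rule does not close: "Concomitant medications that started or stopped on or after day of first dose of study treatment in period 2 are attributed to period 2". A further sentence adds to Period 2 those medications that began before the study and continued into Period 2 or are ongoing.

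On display, the section states "Concomitant medications will be presented by actual treatment group and overall", with the safety population as denominator. SAP 8.1 says that safety data, concomitant medications included, are "summarized by actual treatment (MS1819-SD regardless of period vs. PERT regardless of period").

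Collection runs past treatment. Protocol 8.3.3 and the schedule in SAP 13.2 both record concomitant medications at Visit 10 (Day 56 ± 2), about two weeks after the last study dose. At the end of Visit 9, Protocol 8.3.2 says "All patients are to resume therapy on their prestudy porcine PERT".

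For adverse events, SAP 8.3 closes Period 2 at the end of Period 2 treatment. For a subject who entered both periods, "any event occurring after the end date of the second study period will be considered a follow-up TEAE". It also has a rule for a subject who stops before Period 2.

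**The concern.** A by-treatment medication table is read as showing what patients took while on each treatment. With no end to Period 2 and no follow-up category, the table also takes in medications started after the study treatment was over. In the PERT-MS1819 sequence these land in the MS1819 column, although by then the patient has returned to PERT. An antibiotic course begun in the second week of follow-up would be shown as use during MS1819.

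The adverse event tables treat the same calendar days as follow-up. An event in that interval and the medication given for it would therefore appear in different columns of the same report.

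**Working it through.** The plan gives no figure on this point, so there is none to reproduce. The check compares the rules and then does calendar arithmetic.

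**1. The two attribution rules side by side**

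- Categories: medications have Period 1 and Period 2; adverse events have Period 1, Period 2 and follow-up.
- Upper limit of Period 2: none for medications; end of Period 2 treatment for adverse events.
- Subject who never starts Period 2: for medications, the Period 1 limit is the start of Period 2, which never comes, so Period 1 stays open; for adverse events, later events go to follow-up.
- SAP 3, 8.1 and 11.1 supply no end date or follow-up category for medications.

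**2. How much of the Period 2 window is after treatment**

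Assumptions: each period lasts 21 days and Visit 10 is on Day 56. Share after treatment = follow-up days / (Period 2 days + follow-up days).

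- Period 2 ends Day 43: 56 − 43 = 13 days; 13 / (21 + 13) = 13/34 = 38%.
- Period 2 ends Day 42: 56 − 42 = 14 days; 14 / (21 + 14) = 14/35 = 40%.
- Period 2 ends Day 42, Visit 10 at the edges of its ± 2 day window: 12/33 = 36% and 16/37 = 43%.
- Period 2 moved as a 21-day block to end on Day 41 or Day 45, Visit 10 on Day 56: 15/36 = 42% and 11/32 = 34%.

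At a constant start rate, this is also the share of new starts assigned to Period 2 that begin after treatment. It is not a share of the whole table, which also counts chronic medications carried in from before the study.

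**3. Effect on the two treatment columns**

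Take one subject per sequence, 13 follow-up days, and constant new-start rates m per day on MS1819 and p per day on PERT. After Visit 9 both subjects are on PERT.

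- MS1819 column: 21m + 21m + 13p = 42m + 13p.
- PERT column: 21p + 21p + 13p = 55p.
- Difference: 42m + 13p − 55p = 42(m − p).
- With Period 2 closed at its last dose: 42m against 42p, difference 42(m − p), the same.
- Ratio: (42m + 13p)/(55p) instead of m/p. For an illustrative m = 2p this is 97/55 = 1.76 instead of 2.

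The SAP tabulates subjects, not starts. With illustrative rates m = 0.01 and p = 0.005, the chance of at least one new start is:

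- MS1819 column: average of 1 − exp(−0.21) = 18.9% and 1 − exp(−0.275) = 24.0%, which is 21.5%.
- PERT column: average of 1 − exp(−0.17) = 15.6% and 1 − exp(−0.105) = 10.0%, which is 12.8%.
- Difference: 8.7 points, against 18.9 − 10.0 = 9.0 points with Period 2 closed; 97% is retained. With m = 0.02 and p = 0.01, 94% is retained.

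Both columns rise, their ratio moves toward 1, and the difference hardly changes.

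**4. A second gap in the same rule**

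A medication started during Period 1 and still ongoing at study end meets neither Period 2 sentence. It did not start or stop on or after the first Period 2 dose, and it did not start before the study. It is counted in Period 1 only, although it was taken throughout Period 2. SAP 8.1 treats a missing stop date as ongoing, so records without a stop date fall into the same gap.

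**The case against.** The strongest reply is that little follows from the gap. The table is descriptive, with no planned estimate or test. The medication listing is also planned, so a reader could trace start dates. The table specifications are a separate document not available here and could add a follow-up column. The step from period to treatment column is inferred, since the section speaks both of tabulating for each study period and of presenting by treatment. All of this limits the weight of the point. None of it supplies an end date: attribution by period is the only rule the SAP gives for the by-treatment display.

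Three stronger readings are tempting and should not be drawn.

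- A reader might infer that a true treatment difference is shown at 42/55 = 76% of its size. That needs starts divided by attribution days, which the SAP does not plan. On counts the difference is unchanged, and on subject percentages it is nearly so.
- A reader might infer that resumed PERT would appear under MS1819 for the whole PERT-MS1819 sequence, 15 of 30 completers. That requires resumed PERT to be entered as a new concomitant medication dated after Visit 9. The documents do not say so. The SAP treats PERT as a study treatment and takes prestudy PERT as a baseline characteristic. If PERT were recorded as one continuing prestudy medication, it would reach Period 2 through the sentence on medications begun before the study, and the missing end date would not be the cause.
- A reader might think first of antidiarrheals. Protocol 7.5 prohibits the named symptomatic ones throughout the study, so antibiotics are the better example.

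**Conclusion.** The rule is wrong as written, with a small consequence. Followed exactly, it places medications first started after study treatment in the Period 2 treatment column. In the MS1819-PERT sequence those days are outside the period but still on PERT. In the PERT-MS1819 sequence they are PERT days shown under MS1819.

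About 38% to 40% of the nominal Period 2 window is after treatment, assuming 21-day periods and Visit 10 on Day 56; the date variations above widen this to 34% to 43%. Subject percentages are inflated in both columns and their ratio is pulled toward 1, but the absolute difference in expected starts is unchanged, given constant rates and equal sequences. Separately, Period 2 omits medications begun in Period 1 and never stopped.

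One descriptive safety table is affected. CFA, the noninferiority decision and adverse event attribution are not. Whether resumed PERT would appear under MS1819 cannot be settled from the documents.

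**What to change.** In SAP 8.6.3.1:

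- Attribute a medication to a period only if its use overlaps the interval from the first to the last dose of that period's treatment: it started on or before the last dose, and it stopped on or after the first dose or is ongoing. This closes Period 2 and also captures a medication begun in Period 1 and continuing.
- Place a medication started after the subject's last study dose in a follow-up category, matching SAP 8.3, including for subjects who stop before Period 2.
- State that PERT, whether taken as study treatment or resumed after Visit 9, is not tabulated as a concomitant medication in the treatment columns.

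On the nominal calendar the Period 2 window then falls from 34 to 35 days to 21, the same length as Period 1. The cost is one or two sentences of SAP text and one table column, with no new data.

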- For a missing end day and month where the year is present, the end day and month will be set to the subject's last contact date, unless the year of the subject's last contact date is greater than the end year, in which case the end day and month will be set to December 31st.

To categorize events with partial dates into their associated treatment periods, the imputation rules above will be defined relative to the first dose of the treatment period of interest separately. Thus, in the aforementioned rules, 'study treatment' refers to the treatment in the specified treatment period. Per the imputation rules, events with partial dates may require two imputed start dates to account for each treatment period. For example, an event with missing start day where the start month is the same as the

treatment start month for both study treatments will have the start date imputed to both the treatment start date of the first study period and the treatment start date of the second study period.

Partial and completely missing dates will be imputed for the purposes of classifying concomitant medications as follows:

- Partial dates will be imputed following the same algorithm as above for TEAEs.
- For a missing start date (i.e., day, month, and year are missing), the start date will be set to the date of first dose of study treatment for each period unless the stop date is prior the date of first dose of study treatment for a given period, in which case the start date will be set to the stop date.
- For a missing stop date (i.e., day, month, and year are missing), the medication will be treated as ongoing.

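### As worded, the SAP attributes a medication with a known start in Period 1 and no stop date to Period 1 only, so concomitant use on the second treatment can be undercounted

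*SAP*

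**What the plan says.** SAP 8.6.3.1 gives four attribution sentences, two for each period.

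- **Period 1, first sentence.** Covers medications that "started or stopped on or after day of first dose of study treatment in period 1 and before the start of period 2".
- **Period 1, second sentence.** Covers earlier starts: "Concomitant medications that started prior to the first dose of study treatment in period 1 and stopped on or after day of first dose" (the Period 1 dose is meant), and also those still ongoing.
- **Period 2, first sentence.** "Concomitant medications that started or stopped on or after day of first dose of study treatment in period 2 are attributed to period 2".
- **Period 2, second sentence.** Opens with "Concomitant medications that started prior to the study and are stopped on or after day of first dose of study treatment in period 2" and, after a comma, closes with "or are ongoing, are attributed to period 2".

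SAP 8.1 adds a rule for absent stop dates: "For a missing stop date (i.e., day, month, and year are missing), the medication will be treated as ongoing". Partial dates are imputed by the adverse event algorithm, and a completely missing start date is set to the first dose of each period unless the stop date is earlier.

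Two displays use the attribution. One is by period: "The number and percentage of subjects using prior and concomitant medications will be tabulated for each study period". The other is by treatment: "Concomitant medications will be presented by actual treatment group and overall". The protocol has no period-attribution rule of its own, and SAP section 1 gives the SAP precedence where the two differ.

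**The concern.** The second sentence for Period 1 ties its start condition to the first dose of that period. The matching sentence for Period 2 does not: it refers to the start of the study. That leaves a class of medication with no route into Period 2, namely one begun during Period 1 and never stopped.

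The result runs backwards. A Period 1 start that ends during Period 2 counts in both periods, while a longer exposure that never ends counts in one. It also departs from the SAP's approach to adverse events (section 8.3), where an event present in both periods is attributed to both.

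What is at stake is a descriptive safety table. SAP 8.1 says that summarising by actual treatment is meant to allow comparison of tolerability within the same subject. A reader would use this table to see what else subjects were taking on each treatment. Protocol section 7.5 permits standard-of-care medication such as antibiotics, so new starts during Period 1 are plausible.

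**Working it through.** The plan states no figure on this point, so the check applies the four sentences, as worded, to each feasible combination of start and stop.

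| Start | Stop | Periods in which taken | Attributed to |
|---|---|---|---|
| Before consent | Period 1 | 1 | 1 |
| Before consent | Period 2 | 1 and 2 | 1 and 2 |
| Before consent | Ongoing | 1 and 2 | 1 and 2 |
| Screening | Period 1 | 1 | 1 |
| Screening | Period 2 | 1 and 2 | 1 and 2 |
| Screening | Ongoing | 1 and 2 | 1 and 2 if the study starts at first dose; 1 only if it starts at consent |
| Period 1 | Period 1 | 1 | 1 |
| Period 1 | Period 2 | 1 and 2 | 1 and 2 |
| **Period 1** | **Ongoing** | **1 and 2** | **1 only** |
| Period 2 | Period 2 | 2 | 2 |
| Period 2 | Ongoing | 2 | 2 |

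**The failing row.** The medication has neither a start nor a stop date on or after the first Period 2 dose, so the first Period 2 sentence does not admit it. It did not start before the study, so the second does not either.

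**Missing and partial dates (SAP 8.1).**
- Stop date completely missing: treated as ongoing. No date is supplied, so with a known Period 1 start the case falls in the failing row.
- Stop date partial: imputed. If the imputed date is on or after the first Period 2 dose, the stop limb captures it.
- Start day missing, in a month containing both treatment starts, with no end date: the start is imputed to the first dose of each period, so Period 2 is captured.
- Start date completely missing, medication ongoing: set to the first dose of each period, so Period 2 is captured.

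**Which column loses.** In the MS1819-PERT sequence the missed use belongs to PERT; in the PERT-MS1819 sequence it belongs to MS1819-SD. Subjects count once per ATC term or drug name, so a subject drops out of a row only if no other captured medication falls in it.

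**Scale per subject.** Percentages use the safety population. If that is the 38 subjects planned, one lost subject moves a row by 1/38 = 2.6 percentage points; if it is 30, by 1/30 = 3.3. This is a conversion, not an estimate of how many are lost.

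**After the change.** With the start condition tied to the first Period 2 dose, every row agrees with the periods in which the medication was taken.

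**The case against.** The strongest reply is that the section is coherent only if ongoing is understood as stopping later. Its definition of a concomitant medication mentions starting or stopping on or after the first Period 1 dose and has no ongoing limb. Read strictly, a long-standing medication that is still being taken would be neither prior nor concomitant, yet later sentences treat it as concomitant. If ongoing means stopping later, the first Period 2 sentence already captures the disputed class.

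This shows loose drafting, but it does not close the gap. The first Period 2 sentence already admits any stop on or after the first Period 2 dose, so the only work left for the second sentence is its ongoing clause. On the proposed reading that sentence would do nothing.

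Letting the ongoing clause stand free of the start condition also fails. The same parse of the Period 1 sentence would put medications begun in Period 2 and still ongoing into Period 1.

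The reply is right about scope. Concomitant medications are recorded through Visit 10, so a finite antibiotic course would usually have a stop date and be captured. Protocol 7.5 bars starting CFTR modulators during the study and requires acid suppressants to be on a stable dose from before screening. The screening ambiguity is weak, since the neighbouring rules are tied to first dose. A programmer might also correct the slip unprompted, but the output would then not follow the SAP.

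**Conclusion.** The point holds as a minor error of wording. The rule gives a wrong Period 2 attribution for medications with a known start in Period 1 that are ongoing at last contact or have a completely missing stop date. The by-period and by-treatment tables can therefore understate use on the second treatment, in either sequence. This rests on reading the ongoing clause as governed by the start condition in its own sentence.

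Three stronger readings are tempting and are not supported:

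- **That every Period 1 start with an uncertain stop date is lost.** Partial stop dates are imputed, and some partial or missing start dates are set to the first dose of both periods.
- **That the tables are wrong by a stated amount, or favour one treatment.** The documents do not say how many medications begin in Period 1 and continue. Both treatment columns can lose subjects, and the net direction is unknown.
- **That these medications vanish from the report, or that CFA or adverse event results are affected.** The overall column and the listing still show them. No adverse event or efficacy analysis uses this attribution, and acid suppression enters the CFA model as a separate flag.

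**What to change.** Replace the last attribution sentence of SAP 8.6.3.1 with:

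> For subjects who were dosed in period 2, a concomitant medication that began before the first period 2 dose, and either stopped on or after that day or was still ongoing, is attributed to period 2.

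This mirrors the Period 1 sentence and settles medications begun between consent and first dose. The opening condition keeps ongoing medications of subjects who withdrew in Period 1 out of a period they never entered. The cost is one SAP sentence and about one line of programming. No data collection or clinical procedure changes.
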